### Estimated sample size and power

Based on preliminary results from a nationwide retrospective study (7) and the most recent case series, we assume that the overall 3-year survival to be approximate 40% averaged across both groups. Mariani et al (5) conducted a case control study of a population similar to the inclusion criteria in this study and detected RR 3.04 (CI: 1.87-4.92) in a multivariate cox regression analysis in favour of liver surgery. A smaller reduction of risk is clinically relevant but the challenge of this study is to recruit participants. In order to reach a power of 80 % to detect a hazard ratio of 1.9 with a significance level of 0.05, 190 study participants are required. Under the assumption of a drop-out rate of 5%, we therefore intend to include 200 participants in total. The sample size calculation is made assuming an unadjusted analysis. In the analysis of the primary outcome, model adjustments for baseline covariates will be made (age, molecular subtype of primary tumour, TNM-stage of primary tumour, disease free interval, single or multiple BCLM and presence of bone metastases yes/no). As these covariates are well known prognostic factors, we expect this to give additional gain in power or equivalent opportunity to detect smaller hazard ratios (8). Based on results from a nationwide retrospective study (7) and the most recent case series we assume that the secondary endpoint 3-years survival will be 30% in the control arm (oncological treatment only) and 50% in the treatment arm (surgery and oncological treatment). To reach 80% power with a 5% drop out rate and a level of significance p<0.05, the total study population is calculated to 200 participants also in this analysis.

Isolated oligometastases in the liver affect about 5% of those with advanced breast cancer. This corresponds to 70 patients per year in Sweden. We assume that we can include 50% of these, thus 35 per year. The study will be open for recruitment from centres outside of Sweden with a further specified protocol for surgical and oncological treatment and additional ethical review.

The study will be open for recruitment during 8 years and participants will be followed for at least 3 years. Interim analyses will be performed by the safety committee after inclusion of 100 participants. If the primary endpoint is reached at the interim analysis, the study will be

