stopped and participants in the control arm will be allowed to cross over. If the study reaches a non-significant result in the end of the study it may be prolonged according to a new power calculation and a second ethical review.

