### **Statistical methods**

The primary outcome, time to death for any cause, will be visualized in a Kaplan-Meier plot and analyzed using Cox proportional hazard regression. The null hypothesis to be tested is that the hazard for the intervention group is equal to the hazard of the control group, in a twosided test. A random effects model will be applied with study centre as random effect. Adjustments will be made for age, molecular subtype of primary tumour, TNM-stage of primary tumour, disease free interval, single or multiple BCLM and presence of bone metastases (yes/no) for the purpose of increasing precision and statistical power in analysis. Age will be modelled as a continuous variable using natural cubic splines with three nodes distributed at the 10th, 50th and 90th percentile of the age distribution to account for nonlinear effect. The significance level will be set at 0.05.

Three years survival will be analyzed using logistic regression, adjusted for the same covariates as above,

Progression free survival and breast cancer specific survival will be analyzed using cox regression, as described for the primary outcome.

Predictive factors for survival will be analyzed in a cox proportional hazards model. Quality of life will be analyzed using a ordinal proportional odds regression model.

[name] and statistician at Registercentrum Norr, will be responsible for the statistical analysis plan.

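### The interim efficacy stop with crossover has no defined boundary and is timed by inclusions; if the stated 0.05 is used at both looks, the overall type I error is about 9%

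*Protocol*

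**What the plan says.** In the protocol, the section Estimated sample size and power sets the timing: "Interim analyses will be performed by the safety committee after inclusion of 100 participants". It then gives the condition for an early end: "If the primary endpoint is reached at the interim analysis, the study will be" halted. The consequence for both the trial and its controls is worded as follows: "stopped and participants in the control arm will be allowed to cross over". Project organisation repeats the look at 100 included participants, and gives no boundary there either.

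Statistical methods describes the primary test as a Cox regression whose null hypothesis is that the intervention hazard "is equal to the hazard of the control group, in a twosided test", and adds: "The significance level will be set at 0.05". The sample size rests on the same level: "power of 80 % to detect a hazard ratio of 1.9 with a significance level of 0.05, 190 study participants are required". No other significance level appears in the protocol.

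The sample size section ends by allowing the trial to be prolonged after a non-significant final result, under a new power calculation and a second ethical review. It does not mention the error rate.

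**The concern.** The stop is worded as a requirement, but its criterion is undefined for a time-to-event endpoint. The natural reading is a significant primary test, and the only level on offer is 0.05. That level is already fully committed to the final analysis, so using it twice exceeds 5%.

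The trigger also counts the wrong thing. The information in a survival comparison comes from deaths, and 100 inclusions can correspond to few of them. By Table 1, consent and inclusion take place at the first visit, and randomization at the second liver surgery conference. Between the two come two to three months of oncological treatment (section Oncological treatment), and patients who progress are not randomized.

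At stake is a trial that ends on a false positive or an inflated estimate. Crossover by controls would then weaken the later survival comparison, which is the question the trial exists to answer.

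**Working it through.** **Inputs from the protocol.** Two-sided 0.05; 80% power; hazard ratio 1.9 (control against local treatment); 1:1 allocation; 190 participants, 200 with 5% drop-out; pooled 3-year survival 40%; 3-year survival 30% and 50% by arm for the secondary endpoint; 35 inclusions per year; up to 8 years of recruitment, so 200/8 = 25 per year as a slow bound; at least 3 years of follow-up; look at 100 included.

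**Assumptions.** Exponential survival, uniform accrual, and a lag of 0 to 3 months from inclusion to randomization.

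**1. The plan's own figure.** Schoenfeld: deaths = 4(1.960 + 0.842)²/(ln 1.9)² = 76.2. Then 76.2/0.40 = 190.5, and 190/0.95 = 200. The stated size is reproduced, though only by taking 40% as the proportion dying, which is a separate matter. There is no allowance for an interim: the full 0.05 goes to one test.

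**2. Deaths at the look.** The yearly hazard is −ln(0.40)/3 = 0.305 pooled, or 0.401 and 0.231 by arm. Expected deaths are 100 times the mean of 1 − exp(−hazard × time since randomization) over entry times.

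| Accrual | Time to 100 | Deaths, no lag | Deaths, 3-month lag |
|---|---|---|---|
| 35/year | 2.86 years | 33.3 pooled, 33.6 by arm | 28.3 pooled, 28.7 by arm |
| 25/year | 4.0 years | 42.3 pooled, 42.5 by arm | 37.9 pooled, 38.2 by arm |

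**3. Information fraction.** With 200 participants and the pooled hazard, final deaths are 200 × 0.60 = 120 if everyone is censored at 36 months. If all are followed until 3 years after the last entry, they are about 162 (35/year) to 170 (25/year). The fraction is then 33.3/162 = 0.21 to 33.3/120 = 0.28 at 35/year without lag, and up to 42.3/120 = 0.35 at 25/year.

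**4. Type I error with 0.05 at both looks.** The interim and final Z statistics are bivariate normal with correlation √t, where t is the information fraction. The critical value is 1.96 at each look.

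| t | Stop in either direction | Stop for benefit only, two-sided final | False claim of benefit (nominal 0.025) |
|---|---|---|---|
| 0.20 | 0.092 | 0.071 | 0.046 |
| 0.28 | 0.090 | 0.070 | 0.045 |
| 0.35 | 0.088 | 0.069 | 0.044 |

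The result hardly depends on the death count.

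**5. Prolongation.** Adding a third test at 0.05 after 25% to 100% more deaths (an assumed range), following a non-significant final result, gives a simulated total of about 0.11 to 0.12.

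**6. What would stop the trial.** The observed hazard ratio needed for p<0.05 is exp(1.96 × 2/√d): 2.07 at d = 29 deaths, 1.96 at 34, 1.89 at 38 and 1.83 at 42. The 30%/50% survival figures imply a true ratio of 0.401/0.231 = 1.74. At 30 deaths the expected Z is ln(1.74) × √30/2 = 1.51, so the trial stops about 33% of the time. The average log ratio among those stops is about 0.955, a hazard ratio near 2.6.

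**7. Effect of a strict boundary.** With interim p<0.001 and the final test left at 0.05, the total is 0.0504 to 0.0507. Keeping it at 0.05 needs a final level of 0.0493 to 0.0496. Lan-DeMets O'Brien-Fleming spending gives an interim p of about 0.000001 at t = 0.20, 0.00005 at 0.28 and 0.0003 at 0.35, with the final level at about 0.0499 to 0.0500.

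**The case against.** A reader might infer that the protocol tests the interim at 0.05 and that its error rate therefore is 9%. The text does not say so. The 0.05 in Statistical methods closes the account of the primary analysis and does not mention the interim. A boundary could stand in a statistical analysis plan or committee charter that is not shown, and a strict one would remove nearly all the excess. This stands, and it makes the 9% conditional. It does not clear the rule: the mandatory stop, its trigger and the crossover are all in the protocol, and nothing there refers the boundary to another document.

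Second, crossover by controls makes sense only after a benefit result, so 7% may be the fairer total. That also stands, and both figures are given.

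Third, a reader might put the look at about 20 deaths. That needs substantial loss of patients before randomization, and the protocol gives no such rate. The sample size section may also use inclusion to mean randomization, since the synopsis gives 200 patients as 100 per arm. In that case the counts without lag apply.

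Finally, it would go too far to say that crossover permanently destroys the survival comparison. It is allowed, not required, and the intention-to-treat comparison remains, though diluted.

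**Conclusion.** The concern holds in conditional form. The protocol binds the trial to an efficacy stop on an undefined criterion, timed by inclusions, with the whole two-sided 0.05 already assigned to the final test. If 0.05 is applied at both looks, the total error is about 9%, or about 7% with a benefit-only stop, where false claims of benefit run at about 4.5% against 2.5%. A re-test after prolongation would bring the two-sided total to about 11% to 12%.

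These error rates rest on the joint normal approximation and hold across information fractions of 0.20 to 0.35. The death counts rest on exponential survival and the stated accrual. If no level was intended for the interim, a mandatory stop is left to judgement once the data have been seen, which also needs correcting. Because the stop is hard to reverse and the remedy is cheap, this should be settled before the interim takes place.

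**What to change.** Amend the interim paragraph in Estimated sample size and power, and align Project organisation and the committee charter with it:

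- Replace the undefined criterion with a named efficacy boundary on the primary Cox test. Use either Haybittle-Peto (two-sided p<0.001) with the final test at about 0.049, computed at the actual death fraction, or Lan-DeMets O'Brien-Fleming spending at that fraction. The two are not interchangeable: at a fraction of 0.28 the interim thresholds are 0.001 and about 0.00005.
- State the planned number of deaths at the final analysis and time the efficacy look by a prespecified number derived from it. The protocol's inputs give anything from 120 to about 170 final deaths, depending on how long participants are followed, so this has to be settled first.
- Alternatively, keep the look at 100 participants as safety-only or under the same boundary, and say whether the 100 are included or randomized.
- State that any prolongation after a non-significant final result must keep the overall two-sided error at 0.05.

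The cost is about one paragraph plus matching charter text. The chance of stopping early falls: at 33 deaths, p<0.001 needs an observed hazard ratio of exp(3.29 × 2/√33) = 3.14, against 1.98 for p<0.05. The loss of final power is negligible, since the final level stays between 0.049 and 0.050.

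### Prolonging the trial because the final result is non-significant implies a second test after the first has spent the whole 5%, so the overall type I error exceeds 5%

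*Protocol*

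**What the plan says.** The rule closes the Protocol section Estimated sample size and power: "If the study reaches a non-significant result in the end of the study it may be prolonged according to a new power calculation". The sentence adds one further condition, a second ethical review. The trigger is the result of the end-of-study analysis. No significance level, combination rule or maximum size is attached to the extension.

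Under Statistical methods, the primary outcome (time to death from any cause) is analysed by Cox regression, and equality of hazards is tested "in a twosided test". The level follows: "The significance level will be set at 0.05". No other level appears in the protocol.

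The planned size comes from this statement: "In order to reach a power of 80 % to detect a hazard ratio of 1.9" at the 0.05 level, "190 study participants are required", raised to 200 for drop-out.

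**The concern.** A test at 0.05 leaves nothing for a later test of the same hypothesis. If a second chance is offered only when the first has failed, every additional rejection under the null adds to the 5% already spent. The two conditions in the text do not address this. A power calculation deals with the risk of missing an effect, and an ethical review deals with whether it is acceptable to continue.

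There is also an operational problem. Treatment is visible (liver surgery, ablation or radiotherapy against none), and Variables and measures concedes that radiological assessment cannot be blinded. Extension patients would be recruited and treated by investigators who already know the first result.

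A survival benefit found only after prolongation could then not be reported at the stated 5% level. The situation is realistic: the protocol calls recruitment the challenge of the study and says that risk reductions smaller than the one it is powered for are clinically relevant, so a near miss is plausible.

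**Working it through.** **Inputs from the protocol.** Two-sided level 0.05 (Statistical methods). Extension only after a non-significant end-of-study result (Estimated sample size and power).

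**Assumed, because the protocol does not give them.** The retest uses all accumulated data at 0.05. Total information (in effect, deaths) grows by a factor r, taken from 1.1 to 2 with larger values as a sensitivity check.

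**Step 1: the plan's own figure.** One two-sided test with critical value 1.960 gives P(|Z1| > 1.960) = 0.05. Taken alone, the final test has its stated level. The calculation depends only on the ratio r, so the planned 190 or 200 participants do not enter it.

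**Step 2: final test plus one retest.** Under the null, Z2 = (Z1 + √(r − 1)·W)/√r, where W is an independent standard normal variable. The correlation of Z1 and Z2 is 1/√r. The overall error is

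P(|Z1| > 1.960) + P(|Z1| ≤ 1.960 and |Z2| > 1.960) = 0.05 + added error.

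| r (total information) | Correlation 1/√r | Overall error, all non-significant results extended |
|---|---|---|
| 1.1 | 0.953 | 6.4% |
| 1.25 | 0.894 | 7.1% |
| 1.5 | 0.816 | 7.7% |
| 2 | 0.707 | 8.3% |
| 3 | 0.577 | 8.8% |
| 4 | 0.500 | 9.1% |

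Four million simulated trials gave 7.7% at r = 1.5 and 8.3% at r = 2.

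**Step 3: selective extension.** Suppose that only results with 0.05 < p < 0.20 are extended, so that 1.282 < |Z1| < 1.960. This has probability 0.15 under the null. The overall error is 6.8% at r = 1.25, 6.9% at r = 1.5 and 6.8% at r = 2. At r = 1.5 the added 1.9 points mean that an extended null trial has about a 0.019/0.15 ≈ 13% chance of becoming significant.

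**Step 4: other ways to run the extension.**
- Size set from the observed effect for 80% power, with a cap on r: 7.7% (cap 1.5), 8.3% (cap 2), 9.3% (cap 4), about 10% (cap 10).
- New data tested alone at 0.05: 1 − 0.95² = 9.75%.

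**Step 5: what would restore 5%.** With equal levels at both tests, the nominal two-sided level must be about 0.0347 (r = 1.25), 0.0318 (r = 1.5) or 0.0294 (r = 2). For r = 1.5 the critical value is 2.147. If the trial has exactly the deaths for 80% power at 0.05, power at the first test becomes Φ(1.960 + 0.842 − 2.147) = Φ(0.655) ≈ 74%.

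**The case against.** The strongest reply is that the protocol promises no retest. It says only that "it may be prolonged according to a new power calculation and a second ethical review", so prolongation is optional and the analysis rules could be written when the new approval is sought. Part of this stands: the retest, the pooling of data and the 0.05 level are inferences and should be presented as such. It does not remove the point. A power calculation sizes a hypothesis test, and extending a study on that basis because its test was non-significant has no other evident purpose. Rules written afterwards cannot recover alpha that the final test has already spent. A statistical analysis plan could hold 5% only by lowering the final level or barring a retest, and either would contradict the protocol. Optional use reduces the inflation but does not remove it (Step 3).

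It is also fair that the planned final test, taken alone and setting the interim aside, keeps its level. Only a claim made after prolongation is affected.

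A reader might infer more than the documents support:

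- **Three chances at 0.05, counting the interim.** The protocol states no level and no information fraction for the interim. A combined figure would rest on assumptions about a separate issue.
- **Testing until the result is significant.** The text describes one prolongation after one new review, not unlimited looks.
- **A hazard ratio biased towards benefit.** Extended trials are selected for a non-significant first stage, which pulls their pooled estimate towards the null. The documents do not support a claim of exaggerated benefit.

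**Conclusion.** The point holds in this form. The protocol ties prolongation to a non-significant final result and has already given that final test the full two-sided 0.05. If the extended data are tested again at 0.05, the only level stated, the overall type I error is about 6.4% to 8.3% when all non-significant results are extended (total information up by 10% to 100%). It is about 6.8% to 6.9% when only results with 0.05 < p < 0.20 are extended (information up by 25% to 100%). The growth figures and the p < 0.20 limit are assumptions, because the protocol sets no size and no upper limit on p. The excess is two to three percentage points in most of these cases, and the error is above 5% in all of them. This is a stated rule that conflicts with the stated error rate, not a detail left to an analysis plan.

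**What to change.** Delete the prolongation sentence. State that the analysis at the planned end is the only confirmatory final test and that any longer follow-up or added recruitment is reported descriptively. This costs one sentence and an informal second chance that is not valid as written.

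If room to enlarge is wanted, decide before the final analysis through a review of the pooled number of deaths, blinded to arm, with the rule written in the protocol.

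If an extension after the result is to stay confirmatory, reserve alpha in advance: for example about 0.032 at each of two tests for a 50% extension. Add pre-specified fixed weights (such as an inverse-normal combination) if the size of the extension depends on the data. Fixed weights alone are not enough: with the first test still at 0.05 the two statistics have the joint distribution of Step 2, and the error stays near 7.7% at r = 1.5. The cost is power at the first test, about 74% instead of 80% in the example, or more deaths to recover it.

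The interim analysis without a stated boundary should be handled as its own point.

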### **Statistical methods**

The primary outcome, time to death for any cause, will be visualized in a Kaplan-Meier plot and analyzed using Cox proportional hazard regression. The null hypothesis to be tested is that the hazard for the intervention group is equal to the hazard of the control group, in a twosided test. A random effects model will be applied with study centre as random effect. Adjustments will be made for age, molecular subtype of primary tumour, TNM-stage of primary tumour, disease free interval, single or multiple BCLM and presence of bone metastases (yes/no) for the purpose of increasing precision and statistical power in analysis. Age will be modelled as a continuous variable using natural cubic splines with three nodes distributed at the 10th, 50th and 90th percentile of the age distribution to account for nonlinear effect. The significance level will be set at 0.05.

Three years survival will be analyzed using logistic regression, adjusted for the same covariates as above,

Progression free survival and breast cancer specific survival will be analyzed using cox regression, as described for the primary outcome.

Predictive factors for survival will be analyzed in a cox proportional hazards model. Quality of life will be analyzed using a ordinal proportional odds regression model.

[name] and statistician at Registercentrum Norr, will be responsible for the statistical analysis plan.

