### Variables and measures

Variables are collected in electronic case report forms (CRFs) as in figure 1 and table 1. CRF 1 and 2 are divided into section A and B with variables in A related to liver surgery and in B to breast oncology. CRF 3 and 4 is only for those randomized to local treatment.

CRF1		Registration. Ca 15-3. Performance status. Somatic comorbidities.				
		1a BCLM characteristics				
		1b Breast cancer characteristics and. Oncological and surgical breast cancer treatment of prior to inclusion.				
CRF2		2a Liver metastases after oncological treatment. Evaluations of response according to RECIST 1.1 (9).				
		2b Oncological treatment after inclusion.				
		2c. Result of randomization.				
	Only for thos	se randomized to local treatment				
	CRF3	Local treatment.				
	CRF4	Complications (30-day) according to Clavien-Dindo and the CTC 4.03 scale. Pathological anatomical diagnosis of liver metastases including ER, PgR, Her2. Total number of days at hospital.				
CRF5	Follow up 3, 6, 9, 12, 18, 24, 30, 36 months (5a-h). Oncological treatment and grading of complications by the CTC 4.03 scale. Secondary intervention against metastases. Performance score. Quality of life 3, 12 and 24 months.					
CRF6	Recurrence. Progression.					
CRF7	End of study. Vital status.					

For survival analyses, the primary endpoint is time from randomization to death from any cause. Secondary endpoints are three years overall survival, progression free survival, breast cancer specific survival and median overall survival. Disease progression will be evaluated at each radiology control. This analysis cannot be blinded since radiologists can see signs of previous liver resections. Survival will primarily be evaluated in an intention to treat manner and secondary in a per protocol analysis.

To study safety and complications, 30-days and 90-days mortality after surgery will be determined and complications will be described and graded by the Clavien-Dindo score. Chemotherapy toxicity will be graded by the CTC 4.03 scale.

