To study predictive factors, patient related factors (age and comorbidity), primary tumour related factors (size, histology, molecular subtype) and factors related to the metastatic disease (number, size, locations, molecular subtype, response to treatment, disease free interval) will be related to survival. Hormonal receptor status will enable characterization of the molecular subtype of the primary tumour. To predict outcome, they will be classified according to the St Gallen classification; Luminal A, Luminal B (HER2-positive), Luminal B (HER2-negative), HER2- enriched (non- luminal) and triple-negative breast cancer.

Quality of life will be registered by EORTC QLQ-C30 and QLQ-LMC21 at inclusion, and follow up 3, 12 and 24 months after randomization. QLQ-LMC21 will be added to the study when available in Swedish.

STUDY PLAN	Breast Cancer MDT	1st visit info	1st Liver Surgery MDT	Oncol. treatm.	2nd Liver Surgery MDT	Local treatm. or oncol. treatm.	Postop visit	Follow up 3 months	Follow up 6, 9, 12 months	Follow up 18, 24, 30, 36 months
Time					0			3	6, 9, 12	18, 24, 30, 36
Admission		X		X		X	Х	х	X (12m)	X (24m, 36m)
Randomization					Х					
CRF		1			2	3	4	5 (6, 7)	5 (6, 7)	5 (6, 7)
Informed consent and inclusion		Х								
Randomization					Х					
MRI liver, liver contrast		x			x					
CT thx- abdomen		x			x	X (only liver and only post ablation)		x	x	x
PET-CT		х				, í				
RECIST 1.1					Х					
CA 15/3 (recom- mended)	x					X		X	X (12M)	X (24M)
Biopsy of metastasis	Х									
Histology	х					X (surgery)				
QoL EORTC QLQ C30		X						x	X (12M)	X (24 M)

Table 1.

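### The primary Cox model omits response to pre-randomisation treatment, a baseline covariate already recorded for everyone randomised, and so may forgo a modest gain in power

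*Protocol*

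**What the plan says.** The covariate list of the primary model is given in full in the Protocol, Statistical methods: "Adjustments will be made for age, molecular subtype of primary tumour, TNM-stage of primary tumour, disease free interval, single or multiple BCLM", followed by presence of bone metastases, with study centre as a random effect. The same six covariates stand in Estimated sample size and power. The stated purpose is more precision and power. The logistic model for three-year survival uses the same covariates, and the Cox models for progression-free and breast cancer specific survival follow the primary analysis.

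Response to treatment appears elsewhere. Under Oncological treatment, only patients who are stable or responding go on to randomisation. The CRF table in Variables and measures collects "2a Liver metastases after oncological treatment. Evaluations of response according to RECIST 1.1 (9" in the same form as, and listed ahead of, the randomisation result. Table 1 places the RECIST 1.1 evaluation at the second liver surgery MDT, time 0. The factors to be studied for survival include those of the metastatic disease: "number, size, locations, molecular subtype, response to treatment, disease free interval) will be related to survival".

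**The concern.** If covariates are chosen to gain power, one would expect the list to include a candidate that is measured on everyone at the moment of randomisation. Response is such a candidate. It also describes how the disease behaved under the treatment that decided eligibility, whereas molecular subtype and TNM stage, as listed, describe the primary tumour. Disease free interval stands beside response in the list of factors to be studied and is in the model; response is not.

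In a Cox model, leaving out a prognostic baseline covariate pulls the estimated treatment hazard ratio towards 1 and costs some power. The protocol says that recruitment is the difficulty in this trial, so power from data already collected is worth having. What is at stake is efficiency, not the validity of the test.

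**Working it through.** **Inputs from the Protocol.** Two-sided test ("The null hypothesis to be tested is that the hazard for the intervention group is equal to the hazard of the control group"; "The significance level will be set at 0.05"); 80% power "to detect a hazard ratio of 1.9 with a significance level of 0.05, 190 study participants are required"; "we assume that the overall 3-year survival to be approximate 40% averaged across both groups"; "Under the assumption of a drop-out rate of 5%, we therefore intend to include 200 participants in total"; 1:1 allocation; at least three years of follow-up; sample size based on an unadjusted analysis.

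**Inputs assumed.** The hazard ratio for death, stable versus responding disease, is not in the documents. It is varied from 1.0 to 3.0, with 50% or 30% of patients in the worse-prognosis group.

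**Step 1: the plan's own figure.** Events by Schoenfeld = 4(1.960 + 0.842)² / (ln 1.9)² = 76.2.
- With 40% deaths: 76.2 / 0.40 = 190.5, which matches 190.
- With 60% deaths, which is what 40% survival means: 76.2 / 0.60 = 127.0, which does not match.
- Drop-out: 190 / 0.95 = 200, which matches.

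The stated 190 thus fits only if 40% is read as the proportion dying. That is a separate point. Here it means that both event counts must be carried: 190 × 0.40 = 76 and 190 × 0.60 = 114. Unadjusted power is Φ(√d × ln 1.9 / 2 − 1.960), which gives 79.9% at 76 events and 92.9% at 114.

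**Step 2: the gain from adding response.** Trials of 190 patients were simulated, 1:1, with exponential survival, three years of follow-up and a treatment hazard ratio of 1.9 within response groups. The baseline hazard was set to give 40% or 60% deaths. Each trial was fitted with treatment alone and with treatment plus response, 3,000 trials per row. Power with half the patients in the worse-prognosis group:

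| Response HR (assumed) | 40% deaths: without / with | Gain | 60% deaths: without / with | Gain |
|---|---|---|---|---|
| 1.0 | 79.5% / 79.3% | −0.2 | 93.1% / 92.8% | −0.3 |
| 1.25 | 78.4% / 78.4% | 0.0 | 91.3% / 91.6% | 0.3 |
| 1.5 | 77.4% / 77.9% | 0.5 | 91.9% / 92.4% | 0.5 |
| 2.0 | 76.2% / 78.1% | 1.9 | 90.2% / 92.7% | 2.5 |
| 3.0 | 73.5% / 79.3% | 5.8 | 85.2% / 92.3% | 7.1 |

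Simulation error is about 0.5 to 0.8 points per power figure; the differences are paired and more precise. With 30% in the worse-prognosis group, the gains at response HR 2.0 are 1.9 and 2.1 points, and at 3.0 they are 5.5 and 7.0.

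The fall down the columns without response is not a shortfall against the plan. The simulation holds 1.9 within response groups, whereas the protocol's 1.9 belongs to an unadjusted analysis. Only the difference along a row bears on this point.

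**Step 3: sensitivity to the treatment effect.** The protocol's secondary assumption of 30% versus 50% three-year survival implies ln 0.30 / ln 0.50 = 1.74. At that value, with 60% deaths, power without and with response is 81.3% and 82.7% at response HR 1.5 (gain 1.4), 79.2% and 82.9% at 2.0 (gain 3.7), and 73.7% and 82.4% at 3.0 (gain 8.7). The gains are larger because power is further from its ceiling.

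**Step 4: limit of the comparison.** The simulated comparator has treatment only, while the planned model already has six covariates. Only the part of response not explained by those six would count, so the gains above are more likely too high than too low.

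**The case against.** The strongest reply is that nothing here is wrong. The protocol prespecifies six covariates that it calls well known prognostic factors, and a seventh is a matter of preference. This stands: the omission contradicts no other part of the protocol.

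A reader might infer that the protocol itself calls response prognostic. It does not. The list in Variables and measures is of factors to be studied. It also names comorbidity, primary tumour size, histology, and size and location of metastases, which are outside the model too. What sets response apart is its timing at time 0 and its role in deciding who is randomised, not any effect size in the documents. Excluding progressors also narrows the contrast to stable versus responding disease.

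A reader might also infer that the trial falls below 80% power. The documents do not support this, because the 80% counts no gain from any covariate.

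A third tempting reading is that chance imbalance in response would bias the result, since randomisation is stratified on centre only. With 95 per arm and half responders, the standard error of the difference in proportions is √(2 × 0.25 / 95) = 0.0725, so an imbalance of 10 points or more (1.38 standard errors) arises about 17% of the time. At response HR 2.0 it would shift the log hazard ratio by 0.10 × ln 2 = 0.069, or about 7%. That is ordinary sampling variation, which the test already allows for; the type I error is not inflated. The pull towards 1 is likewise small: at response HR 2.0 and 60% deaths, the mean estimate is 1.84 without response and 1.90 with it.

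Finally, oncological treatment depends on molecular subtype, and its length before randomisation differs between chemotherapy and hormonal therapy. Response will therefore partly reflect regimen and timing and overlap with subtype. This stands as a reason to expect a smaller gain, but not as a reason against a covariate fixed before randomisation.

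**Conclusion.** The point holds as a missed opportunity of low severity. Response is a legitimate baseline covariate, recorded for every randomised patient, and it serves the stated purpose of the adjustment. Leaving it out is not an error, does not bias the test and does not reduce the planned power.

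At the stated treatment hazard ratio of 1.9 with 190 patients, the gain forgone is about 0 to 1 percentage point if response carries a hazard ratio of 1.5 or less, about 2 to 2.5 points at 2.0, and about 5.5 to 7 points at 3.0. The gain is somewhat larger if the true treatment effect is nearer 1.74. All of this rests on an assumed prognostic effect and ignores overlap with the six covariates. To say that the plan gives away power as a matter of fact would go beyond what the documents show.

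**What to change.** Before any outcome data are seen, add one binary covariate to the lists in Estimated sample size and power and in Statistical methods: RECIST 1.1 response at the time-0 evaluation in CRF 2a, stable disease versus partial or complete response. Apply it to the primary Cox model and to the secondary models that use the same covariates. Name the time-0 evaluation rather than best response, because the study plan shows a single RECIST evaluation before randomisation.

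The cost is one degree of freedom against roughly 76 to 114 deaths, with no new data collection. If response turns out not to be prognostic, the simulated change in power is within simulation error (the rows at response HR 1.0). Added after outcome data are known, the same term would be open to challenge as data-driven.
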